Transjugular approach Under the fluoroscopic guidance, an 18-gauge RUPS-100 needle (Rosh-Uchida TIPS set, Cook, Bloomington, USA) will be introduced into the hepatic vein through a long 5-F vascular sheath inserted into the internal jugular vein and punctured through the liver parenchyma from the hepatic vein to the portal vein. When the portal vein is accessed, a hydrophilic guidewire (Terumo, Tokyo, Japan) is used to navigate thrombosed/stenotic segments of portal vein eventually accessing the patent portion of the portal or splenic vein. Next, a portal venogram was performed and the portosystemic pressure gradient (PSG) will be measured. If large varices were identified, coil embolization of esophagogastric varices was performed. The identified occluded portal vein and the intrahepatic tract is dilated using 8 mm/40 mm balloons (PowerFlex, Cordis, Tipperary, Ireland). A ePTFE covered stent (Fluency®, Bard Peripheral Vascular, Tempe, AZ, USA) with a diameter of 8 mm and a length of 6-10 cm will be placed with their proximal end at the hepatocaval junction and their distal end in a patent portion of the portal venous system. If the first stent does not maintain sufficient intra-stent flow, an additional stent will be deployed coaxially. If a large collateral vein was present in patients in whom portal vein recanalisation is not feasible, TIPS placement will be considered to drain blood flow from the large collateral vein to the hepatic vein. The stents will be initially dilated to maximum obtain a good gradient. Finally, the PSG will be remeasured and repeat portography was performed. If residual thrombus remains in the distal end of the stent, an indwelling venous catheter will be

placed in the confluence of the superior mesenteric vein and splenic vein for local thrombolysis with bolus infusions of urokinase (500,000 units twice a day) for 3 days. If the occluded main portal vein or superior mesenteric vein cannot be recanalized or TIPS insertion fails, the patients will be treated with conventional therapy. A Doppler ultrasound was carried out within 2-7 days to evaluate shunt patency.

ET. Patients assigned to the Conventional Therapy group will undergo endoscopic variceal ligation (EVL) within 48 hours of randomization. According to the AASLD practice guidelines for the management of variceal bleeding [3, 26], varices are ligated every 1-2 weeks until they are obliterated or are considered inappropriate for ligation by endoscopists. Endoscopic screening for recurrent varices is arranged within 1-3 months after variceal obliteration, and a repeat endoscopy is then conducted every 6 months. Recurrence of varices was defined as appearance or an increase in the grade of varices after achieving successful eradication or

reduction in size of varices. If varices reappeared, further EVL sessions were initiated.

NSSBs. Patients assigned to the Conventional Therapy group will receive NSSBs immediately after randomization. According to the AASLD practice guidelines for the management of variceal bleeding [3, 26], propranolol should be started at a dose of 20 mg twice a day, and is adjusted to the maximum tolerated dose (160 mg twice a day) or until the heart rate is reduced to 55 b.p.m or 25% from baseline.

Anticoagulation. Patients assigned to the Conventional Therapy group will receive anticoagulants within 2 weeks after variceal obliteration. According to the American College of Chest Physicians (ACCP) guidelines for the management of deep vein thrombosis [27], intravenous infusions of heparin are initially administered at a dose of 1,000 units per hour for 5 days. Subsequently, oral warfarin should be started at a dose of 2.5 mg once a day, and is adjusted to achieve an INR of up to two times the upper limit of normal. Oral warfarin therapy will continue for 6 months or until portal vein complete recanalization.

NSBBs-induced adverse events include lightheadedness, fatigue, and shortness of breath, while the anticoagulant-induced adverse events include bleeding, thrombocytopenia with or without thrombosis, osteoporosis, skin necrosis, alopecia, hypersensitivity reactions, and hypoadosteronism. If adverse events are considered mild or moderate, the treatment will be continued or the dose of these drugs will be reduced until they disappear. If adverse events are considered severe or the patients are unable to tolerate these drugs, the treatment will be discontinued.

TIPS rescue. Patients assigned to the Conventional Therapy group will receive TIPS as a rescue therapy in any one of the following conditions: (1) one episode of clinically significant variceal re-bleeding after endoscopic therapy resulting in the development of hypovolemic shock or a 3 g drop in hemoglobin within any 24 h period if no transfusion is administered [18]; (2) two episodes of clinically significant re-bleeding (i.e., melena or hematemesis); or (3) one episode of clinically significant re-bleeding with pampiniform or racemose varices on endoscopy that are considered inappropriate for ligation or sclerotherapy by endoscopists.

Objectives

Primary objective

To compare the rate of variceal rebleeding between the patients undergoing TIPS and those receiving endoscopic therapy combined with NSSBs and anticoagulants.

Secondary objectives

1. To compare the rate of overall death and variceal bleeding-related death between the two groups.
2. To compare the rate of portal vein recanalization between the two groups.

3. To compare the rate of complications between the two groups.
4. To observe the progression of PVT in patients without portal vein recanalization.

Data collection

Paper case report forms have been designed for data collection by one investigator.

Upon enrollment, the following data will be collected:

1. Demographic characteristics (sex and age).
2. Physical examination parameters (blood pressure, heart rate, height, weight, shifting dullness, hepatomegaly, and splenomegaly).
3. Disease history (the date of diagnosis of liver cirrhosis and PVT, the therapeutic methods of variceal bleeding, viral hepatitis, thrombosis at other sites, alcohol abuse, drug use, abdominal trauma and surgery, hematological disease, the use of oral contraceptives, and other diseases).
4. Laboratory tests (red blood cells, hemoglobin, white blood cells, platelets, total bilirubin, direct and indirect bilirubin, albumin, alanine aminotransferase, aspartate aminotransferase, alkaline phosphatase, glutamine transferase, urea nitrogen, serum creatinine, potassium, sodium, alpha-fetoprotein, prothrombin time, INR, and D-dimer).
5. Electrocardiogram.
6. Anteroposterior chest radiographs.
7. Abdominal CDUS (liver, spleen, grade of ascites [28], and the extension and degree of PVT [24]).
8. Abdominal CT scans (liver, spleen, grade of ascites, and the extension and degree of PVT).

Abbreviations: TIPS, transjugular intrahepatic portosystemic shunt; CT, computed tomography; CDUS, color Doppler ultrasound.

As hepatic encephalopathy occurs, the following data will be collected:

1. The number of episodes of hepatic encephalopathy.
2. The starting time and duration of every episode of hepatic encephalopathy.
3. The grade of every episode of hepatic encephalopathy according to the West Haven Criteria [32].
4. The treatment and outcome of every episode of hepatic encephalopathy.

As shunt dysfunction occurs, the following data will be collected:

1. The number of episodes of shunt dysfunction.
2. The starting time and duration of every episode of shunt dysfunction.
3. The diagnosis, treatment, and outcome of every episode of shunt dysfunction.

As variceal bleeding recurs, the following data will be collected:

1. The number of variceal rebleeds.
2. The starting time and duration of every episode of variceal rebleeding.
3. The causes of every episode of variceal rebleeding.
4. The treatment and outcome of every episode of variceal rebleeding.

As any patient dies, the following data will be collected:

1. The time of death after enrollment.
2. The cause of death.

Reporting of adverse events

An adverse event (AE) is any untoward medical occurrence in a patient or clinical investigation subject administered a pharmaceutical product and which does not necessarily have a causal relationship with this treatment. An adverse event (AE) can therefore be any unfavourable and unintended sign (including an abnormal laboratory finding), symptom, or disease temporally associated with the use of a medicinal (investigational) product, whether or not related to the medicinal (investigational) product.

Serious adverse event (SAE) must be reported to the regulatory authorities immediately (within 24h), whereas **non-serious adverse events** are merely documented in the annual summary sent to the regulatory authority.

Serious adverse event is defined as any untoward medical occurrence when the patient outcome is:

1. **Death** Report if you suspect that the death will be an outcome of the adverse event, and include the date if known.
2. **Life-threatening** Report if suspected that the patient will be at substantial risk of dying at the time of the adverse event, or use or continued use of the device or other medical product might have resulted in the death of the patient.
3. **Hospitalization (initial or prolonged)** Report if admission to the hospital or prolongation of hospitalization will be a result of the adverse event.
4. Emergency room visits that do not result in admission to the hospital should be evaluated for one of the other serious outcomes (e.g., life-threatening; required intervention to prevent permanent impairment or damage; other serious medically important event).
5. **Disability or Permanent Damage** Report if the adverse event resulted in a substantial disruption of a person's ability to conduct normal life functions, i.e., the adverse event resulted in a significant, persistent or permanent change, impairment, damage or disruption in the patient's body function/structure, physical activities and/or quality of life.
6. **Congenital Anomaly/Birth Defect** Report if you suspect that exposure to a medical product prior to conception or during pregnancy may have resulted in an adverse

outcome in the child.

7. **Required Intervention to Prevent Permanent Impairment or Damage (Devices)**
Report if you believe that medical or surgical intervention will be necessary to preclude permanent impairment of a body function, or prevent permanent damage to a body structure, either situation suspected to be due to the use of a medical product.
8. **Other Serious (Important Medical Events)** Report when the event does not fit the other outcomes, but the event may jeopardize the patient and may require medical or surgical intervention (treatment) to prevent one of the other outcomes. Examples include allergic bronchospasm (a serious problem with breathing) requiring treatment in an emergency room, serious blood dyscrasias (blood disorders) or seizures/convulsions that do not result in hospitalization. The development of drug dependence or drug abuse would also be examples of important medical events.

Complication related to treatment

- **Complications related to TIPS** TIPS dysfunction, thrombosis, occlusion/stenosis transcapsular puncture, intraperitoneal bleed, hepatic infarction, fistulae, hemobilia, sepsis, infection of TIPS, hemolysis, encephalopathy, stent migration or placement into IVC or too far into portal vein
- **Complications related to endoscopic therapy:** esophageal stenosis, esophageal ulcers, dysphasia, esophagitis
- **Complications related to NSBB:** dizziness, hypotension, bradycardia, fatigue, shortness of breath, diarrhoea

Sample size calculation

No study has yet compared the outcome between cirrhotic patients with PVT receiving TIPS and those receiving conventional therapy. The sample size was determined on the basis of the results of 12 RCTs in which the rate of variceal bleeding was compared between cirrhotic patients without PVT treated by TIPS and endoscopic therapy (**Table 1**) [33-44]. The pooled rates of variceal rebleeding are estimated to be 20.0% and 43.4% in the TIPS and endoscopic therapy groups, respectively. Notably, bare stents were employed in these 12 RCTs, but covered stents will be used in our study.

Table 1. The rates of variceal rebleeding in cirrhotic patients without portal vein thrombosis treated by TIPS or endoscopic therapy: A review of 12 randomized controlled trials.

First author (Journal, Year)	TIPS group		Endoscopy group	
	Total number of Pts.	Number with variceal rebleeding (%)	Total number of Pts.	Number with variceal rebleeding (%)
Cabrera (Gastroenterology, 1996)	31	7 (22.6%)	32	16 (50%)
Cello (Ann Intern Med, 1997)	24	3 (14.3%)	26	12 (46.2%)
Jalan (Hepatology, 1997)	31	3 (9.7%)	27	14 (51.9%)
Rossle (Lancet, 1997)	61	15 (24.6%)	65	33 (50.8%)
Sanyal (Ann Intern Med, 1997)	41	10 (24.4%)	39	10 (25.6%)
Sauer (Gastroenterology, 1997)	42	6 (14.3%)	41	21 (51.2%)
Merli (Hepatology, 1998)	38	9 (23.7%)	43	22 (51.2%)
Garica-Villarreal (Hepatology, 1999)	22	2 (9.1%)	24	12 (50%)
Narahara (Hepatol Res, 2001)	38	7 (18.4%)	40	13 (32.5%)
Pomier-Layrargues (Gut, 2001)	41	8 (19.5%)	39	22 (56.4%)
Sauer (Endoscopy, 2002)	43	8 (18.6%)	42	13 (31%)
Gulberg (Scand J Gastroenterol, 2002)	28	8 (28.6%)	26	6 (23.1%)

Abbreviation: TIPS, transjugular intrahepatic portosystemic shunt.

Because the rate of shunt dysfunction is lower in patients with covered stents than in those with bare stents [45-46], the rate of variceal rebleeding should be lower in the patients allocated to the TIPS group in our study. On the other hand, given that the rate of variceal bleeding is significantly aggravated by the presence of portal vein thrombosis [5], the rate of variceal rebleeding might be higher in patients allocated to the Conventional Therapy group in our study. Thus, we presume that the rates of variceal rebleeding will be 10% and 45% in TIPS and Conventional Therapy groups, respectively. Considering a type I (α) error of 5%, a type II ($1-\beta$) error of 20%, and a dropout rate of 10%, the total number of patients to be recruited is 50.

Statistical analysis

All data will be analyzed on the intention-to-treat population and supplemented by per-protocol (PP) principles and “as-treated” analysis. In the “as-treated” analysis, patients were analyzed according to the treatment regimen that they received. In addition to the censoring time points in the ITT analysis, patients were censored at the moment they switched therapy. Continuous variables will be summarized as the mean values (\pm standard errors) or the median values (ranges), and will be compared using the independent sample t-test or one-way analysis of variance (ANOVA). Categorical variables will be expressed as frequencies, and will be compared using the Chi-square test or Fisher’s exact test. Cumulative risks will be assessed with Kaplan-Meier curves, and will be compared using the log-rank test. The independent predictors for variceal rebleeding, death, and variceal bleeding-related death will be calculated using the Cox regression model. Two-tailed p-values <0.05 will be considered statistically significant. All statistical calculations will be performed using SPSS 18.0 (Chicago, Illinois, USA) and SAS 8.1 (Cary, North Carolina, USA).

Study implications

PVT increases the rate of variceal rebleeding and mortality in cirrhotic patients [5, 47], thereby negatively changing the natural history of advanced liver cirrhosis [48]. However, no randomized controlled studies have evaluated which treatment modality is preferable to prevent variceal rebleeding in cirrhotic patients with PVT. This study is the first RCT to explore the efficacy of TIPS and conventional therapy for the prevention of variceal rebleeding in such patients. Survival and portal vein recanalization will be compared between patients treated by TIPS and conventional therapy. If TIPS is superior to conventional therapy, TIPS might be recommended as the first-line therapy in these patients. This study will also provide information regarding the natural history of cirrhotic patients with PVT that cannot be recanalized.

References

2. Garcia-Tsao G, Bosch J: Management of Varices and Variceal Hemorrhage in Cirrhosis. *N Engl J Med* 2010, 362:823-832.
4. Bosch J, Garcia-Pagan JC: Prevention of variceal rebleeding. *Lancet* 2003, 361(9361):952-954.
5. D'Amico G, de Franchis R: Upper digestive bleeding in cirrhosis. Post-therapeutic outcome and prognostic indicators. *Hepatology* 2003, 38:599-612.
6. de Franchis R: Revising consensus in portal hypertension: report of the Baveno V consensus workshop on methodology of diagnosis and therapy in portal hypertension. *J Hepatol* 2010, 53(4):762-768.


Summary of changes

1. Any drug planned for encephalopathy prophylactics (arginine, branched-chain amino acids, L-ornithine-L-aspartate) and oral aspirin will not be used in TIPS group because their efficacy is not definite.
2. The time of NSSB administration change from “within 5–7 days after endoscopic therapy” to “immediately after randomization” according to current guidelines.
3. The endoscopic sclerotherapy and cyanoacrylate was abandoned in conventional therapy group.

Statistical Analysis Plan (original version)

Statistical analysis

All data will be analyzed on the intention-to-treat population. Continuous variables will be summarized as the mean values (\pm standard errors) or the median values (ranges), and will be compared using the independent sample t-test or one-way analysis of variance (ANOVA). Categorical variables will be expressed as frequencies, and will be compared using the Chi-square test or Fisher's exact test. Cumulative risks will be assessed with Kaplan-Meier curves, and will be compared using the log-rank test. The independent predictors for variceal rebleeding, death, and variceal bleeding-related death will be calculated using the Cox regression model. Two-tailed p-values <0.05 will be considered statistically significant. All statistical calculations will be performed using SPSS 18.0 (Chicago, Illinois, USA) and SAS 8.1 (Cary, North Carolina, USA).

Statistical Analysis Plan (**Final version**)

Statistical analysis

All data will be analyzed on the intention-to-treat population and supplemented by per-protocol (PP) principles and “as-treated” analysis. In the “as-treated” analysis, patients were analyzed according to the treatment regimen that they received. In addition to the censoring time points in the ITT analysis, patients were censored at the moment they switched therapy. Continuous variables will be summarized as the mean values (\pm standard errors) or the median values (ranges), and will be compared using the independent sample t-test or one-way analysis of variance (ANOVA). Categorical variables will be expressed as frequencies, and will be compared using the Chi-square test or Fisher’s exact test. Cumulative risks will be assessed with Kaplan-Meier curves, and will be compared using the log-rank test. The independent predictors for variceal rebleeding, death, and variceal bleeding-related death will be calculated using the Cox regression model. Two-tailed p-values <0.05 will be considered statistically significant. All statistical calculations will be performed using SPSS 18.0 (Chicago, Illinois, USA) and SAS 8.1 (Cary, North Carolina, USA).

Summary of changes

That “All data will be analyzed on the intention-to-treat population” change to “all data will be analyzed on the intention-to-treat population and supplemented by per-protocol (PP) principles and “as-treated” analysis”.

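### Kaplan-Meier is the only cumulative-risk method planned and no competing-risk method is given, so reported absolute risks of rebleeding and bleeding-related death would be too high wherever patients die of something else first

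*Supplement*

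**What the plan says.** The final SAP (Statistical analysis), repeated in the same section of the final protocol, states: "Cumulative risks will be assessed with Kaplan-Meier curves, and will be compared using the log-rank test". That sentence names no endpoint. The next one shows which outcomes are handled as times to event: "The independent predictors for variceal rebleeding, death, and variceal bleeding-related death will be calculated using the Cox regression model".

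The primary objective is "To compare the rate of variceal rebleeding between the patients undergoing TIPS and those receiving endoscopic therapy combined with NSSBs and anticoagulants". The first secondary objective is "To compare the rate of overall death and variceal bleeding-related death between the two groups". Neither names a time point or a method. For frequencies the SAP adds: "Categorical variables will be expressed as frequencies, and will be compared using the Chi-square test or Fisher’s exact test".

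The only mention of censoring belongs to the as-treated analysis: "In addition to the censoring time points in the ITT analysis, patients were censored at the moment they switched therapy". The intention-to-treat censoring points that it refers to are not listed. Nothing in the final protocol or final SAP says what happens to a patient who dies without rebleeding. No cumulative incidence function, Gray's test, subdistribution model or composite with death appears. Time and cause of death are collected (final protocol, Data collection).

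**The concern.** A patient who dies without rebleeding can no longer rebleed. A patient who dies of liver failure can no longer die of bleeding. Kaplan-Meier with these deaths censored treats such patients as still able to have the event later. One minus Kaplan-Meier then describes a setting in which nobody dies of anything else. It does not describe the share of randomized patients who have the event.

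Of the three outcomes in the Cox sentence, only overall death is free of this problem. Competing death is plausible in this population. The final protocol's Study implications section says that portal vein thrombosis raises mortality, Child-Pugh C is a randomization stratum, and the Background describes procedural complications of TIPS as possibly fatal.

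What is at stake is the reported size of the risks and of their difference. Study implications says that a superior result might support TIPS as first-line therapy. That judgement weighs absolute bleeding benefit against harm, so the absolute risks need to be right.

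**Working it through.** **Inputs from the documents.** Planning rates (Sample size calculation): "we presume that the rates of variceal rebleeding will be 10% and 45% in TIPS and Conventional Therapy groups, respectively". Alpha: "Two-tailed p-values <0.05 will be considered statistically significant". Power 80%, dropout 10%, total 50, allocation 1:1.

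**Assumptions, because the documents give no figure.** Constant hazards over follow-up; net risk of death without rebleeding D of 10-40%.

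**Step 1: reproduce the plan's own figure.** Two proportions, unpooled variance:

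n = (1.960 + 0.842)² × (0.10×0.90 + 0.45×0.55) / 0.35² = 21.6, so 22 per arm. 22/0.9 = 24.4, so 25 per arm and 50 in total. The plan's figure is reproduced. It comes from a comparison of proportions and does not depend on the Kaplan-Meier question.

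**Step 2: from Kaplan-Meier risk to cumulative incidence.** Let F be one minus Kaplan-Meier for rebleeding, λb = −ln(1−F) and λd = −ln(1−D). Then

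CIF = λb/(λb+λd) × [1 − (1−F)(1−D)].

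Example with D = 20%, λd = 0.2231:
- Conventional therapy, F = 45%, λb = 0.5978: 0.5978/0.8210 × (1 − 0.55×0.80) = 0.728 × 0.56 = 40.8%.
- TIPS, F = 10%, λb = 0.1054: 0.1054/0.3285 × (1 − 0.90×0.80) = 0.321 × 0.28 = 9.0%.

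Equal D in both arms:

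| D | TIPS | Conventional | Difference (points) | Excess in the Kaplan-Meier difference of 35 |
|---|---|---|---|---|
| 0% | 10.0% | 45.0% | 35.0 | 0 |
| 10% | 9.5% | 42.9% | 33.4 | 1.6 |
| 20% | 9.0% | 40.8% | 31.8 | 3.2 |
| 30% | 8.4% | 38.5% | 30.1 | 4.9 |
| 40% | 7.9% | 36.1% | 28.3 | 6.7 |

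**Step 3: unequal mortality.**

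| D, TIPS | D, conventional | Difference in cumulative incidence (points) | Excess in the Kaplan-Meier difference |
|---|---|---|---|
| 10% | 40% | 26.6 | 8.4 |
| 40% | 10% | 35.1 | −0.1 |
| 20% | 0% | 36.0 | −1.0 |
| 40% | 0% | 37.1 | −2.1 |

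Kaplan-Meier never understates the risk within an arm. The bias in the difference depends on deaths by arm.

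**Step 4: bleeding-related death.** The Background gives nearly 20% mortality per rebleeding episode. Taking 20% of 10% and of 45% as illustrative net risks gives 2% against 9%, a difference of 7.0 points. Here D is other-cause death. At D = 10% the cumulative incidences are 1.90% and 8.55% (6.65 points). At D = 40% they are 1.57% and 7.08% (5.51 points).

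**Step 5: is the log-rank test distorted?** Simulation with 23 per arm (25 less about 10%) and 6,000 runs, deaths censored. With equal rebleeding hazards (45% net risk in both arms), type I error was 5.1% with deaths 20%/20% (TIPS/conventional), 5.4% with 40%/10% and 5.1% with 10%/40%. With 10% against 45%, power was 79% without deaths, 76% at 20% deaths in each arm and 69% at 40%. Competing deaths remove events but do not bias the test of the cause-specific hazard.

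**The case against.** The strongest case on the other side has four parts.

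- **The link to the primary endpoint is inferred.** The Kaplan-Meier sentence names no endpoint, the primary objective speaks of a rate, the sample size comes from two proportions, and Chi-square or Fisher tests are planned for frequencies. If the primary comparison is of crude proportions, this bias does not arise there. That is correct, but it does not remove the point. The SAP assigns cumulative risks to Kaplan-Meier, treats rebleeding and bleeding-related death as times to event, and does not say which comparison is primary.
- **Censoring at death is inferred.** A reader might take it as the SAP's stated rule. It is only the usual default, since the SAP does not list its censoring points. The silence is itself part of what needs mending.
- **The log-rank test is sound.** A reader might infer that log-rank and Cox are invalid here and that Gray's test must replace them. Step 5 does not support that. Both remain valid for the cause-specific hazard. Gray's test answers a different question and also responds to treatment effects on death.
- **The size is assumed and modest.** The 10-40% range has no source in the documents. The per-episode mortality of nearly 20% concerns deaths after a rebleed, which do not compete with a first one. The exclusions for malignancy or other life-shortening illness, renal insufficiency, severe cardiopulmonary disease and sepsis would tend to lower other-cause mortality. With 25 per arm, the 95% half-width of the difference is 1.96 × √(0.10×0.90/25 + 0.45×0.55/25) = 22.8 points, far more than a shift of 1.6-6.7 points. This stands and bears on severity. Unlike sampling error, though, the within-arm bias has a known direction and can be avoided with data already collected.

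**Conclusion.** The concern holds as a fault in how absolute risks would be estimated. If deaths are censored in the usual way, one minus Kaplan-Meier overstates the risk of rebleeding and of bleeding-related death in any arm with competing deaths. At an assumed equal D of 10-40% under constant hazards, the overstatement for rebleeding is 2.1-8.9 points with conventional therapy (45 − 42.9 to 45 − 36.1), 0.5-2.1 points with TIPS (10 − 9.5 to 10 − 7.9) and 1.6-6.7 points in the 35-point difference.

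A reader might go further and conclude that the absolute benefit of TIPS is bound to be overstated. The documents do not support that. They give no mortality by arm, and the bias in the difference vanishes at about 40% TIPS against 10% conventional and reverses at 20% against 0%. The Background's remark that TIPS has not improved survival in cirrhosis makes equal mortality a fair base case. It refers to cirrhosis in general, however, and does not establish mortality in this trial.

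The significance test and the sample size of 50 are not invalidated. This should be fixed, but the trial's main conclusion does not hang on it.

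**What to change.** Amend the final SAP as follows, and repeat the text in the protocol's Statistical analysis section.

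1. List the intention-to-treat censoring points and say how a death without rebleeding is handled.
2. For rebleeding and bleeding-related death, replace one minus Kaplan-Meier with Aalen-Johansen cumulative incidence. The competing event is death without rebleeding for the former and death from any other cause for the latter. Report the difference between arms at a named time with its 95% CI.
3. Keep log-rank and Cox for these endpoints, labelled as comparisons of cause-specific hazards. Gray's test may be added as a supplement.
4. Keep Kaplan-Meier and log-rank for overall death.

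The cost is about one paragraph and a little more analysis work. Time and cause of death are already collected, so no new data are needed. The team should confirm that the software named in the SAP can produce the estimator. The reported rebleeding risks will be slightly lower than under Kaplan-Meier. No change to the sample size follows.
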